3.2 DISCUSSION OF TRIAL DESIGN, INCLUDING THE CHOICE OF CONTROL GROUP(S)

This trial is designed to confirm that the highest dose of BI765128 can be used for further testing in phase IIb trials. The trial consists of separate parts, A and B. The SRD dose escalation part is included and was designed with the goal to minimize the number of subjects exposed to subtherapeutic doses while on the other hand preserving safety and rapid dose finding. This part of the trial will enrol subjects with DMI as IVT injections in healthy subjects would not be considered ethical. Dose escalation and cohort size will be decided by the SMC, guided by a BLRM with overdose control. An EWOC design will increase the chance of treating subjects at efficacious doses while reducing the risk of overdosing. The use of BLRM for Phase I studies has also been advocated by the European Medicines Agency (EMA) guideline on small populations [[R07-4856](#)] and by the Food and Drug Administration (FDA) [[R13-4881](#)].

Part B will consist of a MD cohort [REDACTED] and will start after Part A. Subjects will either be randomized to the active treatment group or to a sham control group (ratio 2:1). This part of the trial will generate additional safety data after multiple dosing and allow for exploration of the time course and durability of treatment effects. This data will further inform the injection frequency and intervals in later studies.

An extended SMC will be established for both part A and part B. The SMC shall operate under the principles specified in the SMC charter. The primary objective of the SMC is to ensure and protect the safety and well-being of the trial subjects and to regularly review the trial data and provide recommendation for the further conduct of the trial (see section [8.7](#)).

3.3 SELECTION OF TRIAL POPULATION

This trial will recruit up to 48 subjects in total; up to 18 subjects in Part A (depending on the dose escalation) and 30 subjects in Part B. In Part B subjects will be randomized to receive either active IVT injection or sham injection.

Screening of subjects for this trial is competitive, i.e. screening for the trial will stop at all sites at the same time once a sufficient number of subjects have been screened. Investigators will be notified about screening completion and will then not be allowed to screen additional subjects for this trial.

A log of all subjects enrolled into the trial (i.e. who have signed informed consent) will be maintained in the Investigator Site File (ISF) at the investigational site irrespective of whether they have been treated with the investigational drug or not.

Subjects who do not fulfil all eligibility criteria for a reason that later resolves allowing eligibility criteria to be met after the initial screening visit, can be re-screened up to one time.

If a subject is entered in error (does not meet all inclusion criteria or meets one or more exclusion criteria on the day of enrolment), the sponsor has to be contacted immediately. It is planned to conduct the trial in up to 3-6 countries and at approximately 50 sites.

3.3.1 Main diagnosis for trial entry

Diabetic macular ischemia (DMI) in patients previously treated with Panretinal photocoagulation (PRP) for diabetic retinopathy (DR)

Please refer to section [8.3.1](#) (Source Documents) for the documentation requirements pertaining to the in- and exclusion criteria.

3.3.2 Inclusion criteria

Part A

1. Panretinal photocoagulation-treated DR patients with either no or inactive retinal neovascularization per investigator judgement in the study eye
2. Male or female subjects of age ≥ 18 years
3. Evidence of DMI per investigator's judgement, defined as any degree of disruption of retinal vascularity in OCTA
4. HbA1c of $\leq 12.0\%$
5. Best-corrected VA ≤ 75 letters (20/32) in the study eye
6. Best corrected VA in the non-study eye must be equal to or better than best corrected VA in the study eye. If both eyes are eligible (per inclusion #5) and have identical best corrected VA the investigator may select the study eye.
7. Women of childbearing potential (WOCBP) and men able to father a child must be ready and able to use two methods of contraception with at least one of them being a highly effective method of birth control per ICH M3 (R2) that result in a low failure rate of less than 1% per year when used consistently and correctly. A list of

contraception methods meeting these criteria is provided in the patient information in Section 4.2.2.3.

8. Signed and dated written informed consent in accordance with ICH GCP Harmonized Guideline for Good Clinical Practice and local legislation prior to admission to the trial

¹ A woman is considered of childbearing potential (WOCBP), i.e. fertile, following menarche and until becoming postmenopausal unless permanently sterile. Permanent sterilisation methods include hysterectomy, bilateral salpingectomy and bilateral oophorectomy. Tubal ligation is NOT a method of permanent sterilisation. A postmenopausal state is defined as no menses for 2 years without an alternative medical cause. A high follicle stimulating hormone (FSH) level in the postmenopausal range may be used to confirm a post-menopausal state in women not using hormonal contraception or hormonal replacement therapy. However, in the absence of 2 years of amenorrhoea, a single FSH measurement is insufficient.

Part B

1. Panretinal photocoagulation-treated DR patients with either no or inactive retinal neovascularization per investigator judgement
2. Male or female subjects of age ≥ 18 years
3. Presence of significant DMI: Large foveal avascular zone (FAZ) defined as those with $\geq 0.5\text{mm}^2$ area present on OCTA. If FAZ is $< 0.5\text{mm}^2$ then an enlarged peri-foveal inter-capillary space in at least 1 quadrant will be sufficient.
4. HbA1c of $\leq 12.0\%$
5. Best-corrected VA ≤ 85 letters (20/20) in the study eye
6. If both eyes are eligible, the investigator may select either eye to be the study eye.
7. Women of childbearing potential (WOCBP) and men able to father a child must be ready and able to use two methods of contraception with at least one of them being a highly effective method of birth control per ICH M3 (R2) that result in a low failure rate of less than 1% per year when used consistently and correctly. A list of contraception methods meeting these criteria is provided in the patient information in Section 4.2.2.3.
8. Signed and dated written informed consent in accordance with ICH GCP Harmonized Guideline for Good Clinical Practice and local legislation prior to admission to the trial

¹ A woman is considered of childbearing potential (WOCBP), i.e. fertile, following menarche and until becoming postmenopausal unless permanently sterile. Permanent sterilisation methods include hysterectomy, bilateral salpingectomy and bilateral oophorectomy. Tubal ligation is NOT a method of permanent sterilisation. A postmenopausal state is defined as no menses for 2 years without an alternative medical cause. A high follicle stimulating hormone (FSH) level in the postmenopausal range may be used to confirm a post-menopausal state in women not using hormonal contraception or hormonal replacement therapy. However, in the absence of 2 years of amenorrhoea, a single FSH measurement is insufficient.

3.3.3 Exclusion criteria

Part A:

1. Subjects receiving IVT injections for active Diabetic Macular Edema (DME) (anti-VEGF, steroids) and macular laser in the previous 3 months to screening in the study eye
2. Subjects receiving anti-VEGF IVT injections for active DR in the previous 3 months to screening in the study eye
3. Current or planned use of medications known to be toxic to the retina, lens or optic nerve (e.g. desferoxamine, chloroquine/hydrochloroquine, chlorpromazine, phenothiazines, tamoxifen, nicotinic acid, and ethambutol)
4. Additional progressive eye disease in the study eye that could compromise best corrected VA (BCVA), uncontrolled glaucoma (IOP>24), history of high myopia > 8 diopters in the study eye. Anterior segment and vitreous abnormalities in the study eye that would preclude adequate observation with SD-OCT and OCTA.
5. Any intraocular surgery in the study eye within 3 months prior to screening
6. Glaucoma tube shunts
7. Aphakia or total absence of the posterior capsule. Yttrium aluminum garnet (YAG) laser capsulotomy permitted, if completed more than 3 months prior to screening, in the study eye
8. Subjects not expected to comply with the protocol requirements or not expected to complete the trial as scheduled (e.g. chronic alcohol or drug abuse or any other condition that, in the investigator's opinion, makes the subject an unreliable trial subject)
9. Previous participation in this trial or in other trials with IVT injections administered within 3 months of screening. Subjects enrolled in trial 1436-0001 SRD part (after five half-lives since the last trial dose, if the participants were not discontinued from study due to safety reasons, and if no toxicity, adverse events or safety concerns related to the previous participation are present at the time of screening) and sham arm in the MD part may be enrolled into Part A of this trial.
10. Significant disease or other medical conditions* (as determined by medical history, examination and clinical investigations at screening) that may, in the opinion of the investigator result in any of the following:
 - a) Putting the subject at risk because of participation in this study
 - b) Influence the results of this study
 - c) Cause concern regarding the subject's ability to participate in the study
11. Known hypersensitivity to any of the ingredients used in the investigational medicinal product (IMP) formulation
12. Active intraocular inflammation in the study eye
13. Active infectious conjunctivitis in either eye
14. Women who are pregnant, nursing, or who plan to become pregnant while in the trial

*e.g. cardiac (including tachycardia), gastro-intestinal, hepatic, renal, metabolic, dermatologic, neurological, haematological, oncological and psychiatric. Subjects with malignancy for which the subject has undergone resection, radiation or chemotherapy within past 5 years. Subjects with treated basal cell carcinoma or fully cured squamous cell carcinoma are allowed.

Part B:

1. Diabetic Macular Edema (DME), defined as a CST $\geq 305\mu\text{m}$ for men and $\geq 290\mu\text{m}$ for women (Optovue Angiovue) in the study eye
2. Subjects receiving IVT injections for active DME (anti-VEGF, steroids) and macular laser in the previous 3 months to screening in the study eye
3. Subjects receiving anti-VEGF intravitreal IVT injections for active DR in the previous 3 months to screening in the study eye
4. Heavily lasered macula in the study eye per investigator judgement
5. History of vitrectomy in the study eye
6. Epiretinal membrane with extended foveal contour distortion in the study eye
7. Current or planned use of medications known to be toxic to the retina, lens or optic nerve (e.g. desferoxamine, chloroquine/hydrochloroquine, chlorpromazine, phenothiazines, tamoxifen, nicotinic acid, and ethambutol)
8. Additional eye disease in the study eye that could compromise best corrected VA (BCVA). Significant visual field loss, uncontrolled glaucoma (IOP>24), clinically significant diabetic maculopathy, history of ischemic optic neuropathy or retinal vascular occlusion, symptomatic vitreomacular traction, or genetic disorders such as retinitis pigmentosa; history of high myopia > 8 diopters in the study eye. Anterior segment and vitreous abnormalities in the study eye that would preclude adequate observation with SD-OCT and OCTA
9. Any intraocular surgery in the study eye within 3 months prior to screening
10. Glaucoma tube shunts
11. Aphakia or total absence of the posterior capsule. Yttrium aluminum garnet (YAG) laser capsulotomy permitted, if completed more than 3 months prior to screening in the study eye
12. Subjects not expected to comply with the protocol requirements or not expected to complete the trial as scheduled (e.g. chronic alcohol or drug abuse or any other condition that, in the investigator's opinion, makes the subject an unreliable trial subject)
13. Previous participation in this trial or in other trials with IVT injections administered within 3 months of screening. Subjects enrolled in the sham arm of the MD part of trial 1436-0001 may be enrolled into Part B of this trial.
14. Significant disease or other medical conditions* (as determined by medical history, examination and clinical investigations at screening) that may, in the opinion of the investigator result in any of the following:
 - a. Put the subject at risk because of participation in the study
 - b. Influence the results of the study
 - c. Cause concern regarding the subject's ability to participate in the study
15. Known hypersensitivity to any of the ingredients used in the IMP formulation
16. Active intraocular inflammation in the study eye
17. Active infectious conjunctivitis in either eye
18. Women who are pregnant, nursing, or who plan to become pregnant while in the trial

*e.g. cardiac (including tachycardia), gastro-intestinal, hepatic, renal, metabolic, dermatologic, neurological, haematological, oncological and psychiatric. Subjects with malignancy for which the subject has undergone resection, radiation or chemotherapy within past 5 years. Subjects with treated basal cell carcinoma or fully cured squamous cell carcinoma are allowed.

3.3.4 Withdrawal of subjects from treatment or assessment

Subjects may discontinue trial treatment or withdraw consent to trial participation as a whole ('withdrawal of consent') with very different implications; please see Sections 3.3.4.1 and 3.3.4.2 below.

Every effort should be made to keep the subjects in the trial: if possible, on treatment, or at least to collect important trial data.

Measures to control the withdrawal rate include careful subject selection, appropriate explanation of the trial requirements and procedures prior to trial enrolment and first administration of trial medication, as well as the explanation of the consequences of withdrawal.

The decision to discontinue trial treatment or withdraw consent to trial participation and the reason must be documented in the subject files and CRF. If applicable, consider the requirements for Adverse Event collection reporting (please see sections [5.2.7.1](#) and [5.2.7.2](#)).

3.3.4.1 Discontinuation of trial treatment

An individual subject will discontinue trial treatment if:

1. The subject wants to discontinue trial treatment, without the need to justify the decision.
2. The subject has repeatedly shown to be non-compliant with important trial procedures and, in the opinion of both, the investigator and sponsor representative, is not willing or able to adhere to the trial requirements in the future.
3. The subject needs to take concomitant medication that interferes with the investigational medicinal product or other trial treatment.
4. The subject can no longer receive trial treatment for medical reasons (such as surgery, adverse events, other diseases, or pregnancy). An AE or clinically significant laboratory change or abnormality occurs that the investigator judge to warranting discontinuation of treatment

If new efficacy/safety information becomes available, Boehringer Ingelheim will review the benefit-risk-assessment and, if needed, pause or discontinue the trial treatment for all subjects or take any other appropriate action to guarantee the safety of the trial subjects.

Even if the trial treatment is discontinued (Part B), the subjects remain in the trial and, given their agreement, will undergo the procedures for early treatment discontinuation and follow-up as outlined in the [Flow Chart II](#) and section [6.2.3](#).

3.3.4.2 Withdrawal of consent to trial participation

Subjects may withdraw their consent to trial participation at any time without the need to justify the decision.

If a subject wants to withdraw consent, the investigator should be involved in the discussion with the subject and explain the difference between trial treatment discontinuation and withdrawal of consent to trial participation, as well as explain the options for continued follow-up after trial treatment discontinuation, please see section [3.3.4.1](#).

3.3.4.3 Discontinuation of the trial by the sponsor

Boehringer Ingelheim reserves the right to discontinue the trial overall or at a particular trial site at any time for the following reasons:

1. Failure to meet expected enrolment goals overall or at a particular trial site.
2. New efficacy or safety information invalidating the earlier positive benefit-risk-assessment, please see section [3.3.4.1](#).
3. Deviations from GCP, the trial protocol, or the contract impairing the appropriate conduct of the trial.

For the following scenario further enrolment and entering in part A and further treatments in part B will be interrupted by the sponsor once the sponsor becomes aware (i.e. stopping rule):

- A single serious adverse reaction (i.e. a single serious adverse event) or two severe adverse reactions in two different subjects (regardless of the system organ class) confirmed by both the investigator and sponsor as having a reasonable causal relationship to the IMP administration.

If the trial stops because one of the stopping rules is triggered, then the trial re-start will only be possible after regulatory authority approval via a substantial amendment.

Further follow up of subjects affected will occur as described in section 3.3.4.1.

The investigator / the trial site will be reimbursed for reasonable expenses incurred in case of trial termination (except in case of the third reason).

3.3.5 Replacement of subjects

Part A:

Subjects withdrawn before visit 4 for another reason than DLE or subjects who miss any visit from Visit 2 up to and including Visit 4 are not evaluable for the occurrence of a DLE within 7 days after drug administration. These subjects will be replaced if not decided otherwise by the SMC. Subjects who come off study due to a DLE will not be replaced.

Part B:

If some subjects do not complete the trial, the Clinical Trial Leader together with the Trial Pharmacokineticist and the Trial Statistician are to decide, if and how many subjects will be replaced. A replacement subject will be assigned a unique trial subject number and will be assigned to the same treatment as the subject he or she replaces.

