3. DESCRIPTION OF DESIGN AND TRIAL POPULATION

3.1 OVERALL TRIAL DESIGN

This trial will consist of two parts, A and B. Part A will be non-randomized, open-label and uncontrolled. Part B will be double-masked, randomized and sham-controlled. One eye will be selected, according to inclusion /exclusion criteria, as the study eye to be treated.

Part A:

Cohorts of subjects will receive escalating doses of BI 765128, [REDACTED]

For any dose-escalation cohort, at least 3 evaluable subjects will be required. Each cohort will consist of newly enrolled subjects.

Dosing of subjects will be done in the following order:

Cohort 1, [REDACTED] (number=3):

- 28 days after subject 1 of the first dose group is dosed, subject 2 of the first dose group can be dosed, if there is no ocular inflammation in the study eye requiring treatment
- 28 days after subject 2 of the first dose group is dosed, subject 3 of the first dose group can be dosed if there is no ocular inflammation in the study eye requiring treatment
- 14 days after subject 3 of the first dose group is dosed, the first subject of the next dose group can be dosed (If no there is no ocular inflammation in the study eye requiring treatment, and if the SMC decides it is safe to go to the next dose group)

Cohort 2, [REDACTED] (number=3):

- 14 days after subject 1 of the second dose group is dosed, subjects 2 and 3 of the second dose group can be dosed (if there is no ocular inflammation in the study eye requiring treatment)
- 14 days after the third subject is dosed, the first subject of the next dose group can be dosed, if there is no ocular inflammation in a study eye requiring treatment, and if the SMC decides it is safe to go to the next dose cohort

Cohort 3, [REDACTED] (number=6):

- 14 days after subject 1 of the third dose group is dosed, subjects 2,3,4,5 and 6 of the third dose group can be dosed, if there is no ocular inflammation in a study eye requiring treatment
- 14 days after the final subject has been dosed, Part B of the trial can start, if there is no inflammation in a study eye requiring treatment, and if the SMC decides it is safe to do so.

A Safety Monitoring Committee (SMC) will be established to regularly review the data and to provide recommendation for the further conduct of the trial.

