After each subject has completed visit 4 follow-up assessments (7 days after drug administration), the dosing investigator will complete the 'DLE Safety Review Form' to summarise the key safety findings for the subject. Once completed, the site will send the form to the CTM and CTL.

First 2 subjects in cohort 1 ([REDACTED])

Once the first two subjects have attended visit 6 (day 29), each dosing investigator will complete the 'Ocular Inflammation Review forms'.

Subsequent subjects in part A

Once the following subjects have attended visit 5 (day 15), each dosing investigator will complete an 'Ocular Inflammation Review form' to identify any ocular inflammation. Once completed, the site will send the form to the CTM and CTL. Once the last subject in each cohort has attended visit 5 (day 15), the CTL will forward the 'DLE Safety Review Forms' and the 'Ocular Inflammation Review Forms' for that cohort to other members of the SMC to carefully evaluate all available systemic (i.e. physical examinations, safety lab parameters, ECG and AEs) and ophthalmological (i.e. as defined in section 5.2.1 of the CTP (DLEs)) safety data. The SMC will meet after the last subject of each dose cohort has attended visit 5.

A Bayesian logistic regression model (BLRM), based on a weakly informative prior distribution, and employing the escalation with overdose control (EWOC) principle (see Section 7) will be used for guiding the dose escalation [R13-4803]. After all subjects in a cohort have either experienced a DLE or have been observed for at least the 7 days evaluation period without experiencing a DLE (i.e. 7 days after drug administration, until visit 4, will be evaluated per subject), the BLRM will be updated with the newly accumulated data. The overdose risk will then be calculated for each dose, and escalation will be permitted to all planned doses which fulfil the EWOC criterion and the respective escalation rule.

The BLRM provides estimates for the probability of observing a DLE for each planned dose. Dose escalation will be permitted to the next planned dose which fulfils the EWOC criterion. Note that this may also result in repeating the current dose level, or in going down to a lower dose level again.

If DLEs are observed in the first two consecutive subjects of a previously untested dose level, subsequent enrolment to that cohort will be stopped.

The MFD may be considered reached if all of the following criteria are fulfilled:

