7.1 STATISTICAL DESIGN – MODEL

This trial will consist of a Part A followed by a Part B. The Part A will be conducted non-randomized, open-label, and uncontrolled. Part B will be conducted double-masked randomized and sham-controlled.

Part A:

The dose escalation will be guided by a Bayesian 2-parameter logistic regression model with overdose control [R13-4803, R13-4806].

The model is given as follows:

$$\text{logit}(\pi_d) = \log(\alpha) + \beta \cdot \log(d/d^*),$$

where $\text{logit}(\pi) = \log(\pi/(1-\pi))$, π_d represents the probability of having a DLE in the evaluation period at dose d , $d^* = \blacksquare$ mg is the reference dose, allowing for the interpretation of α as the odds of a DLE at dose d^* , and $\theta = (\log(\alpha), \log(\beta))$ with $\alpha, \beta > 0$ is the parameter vector of the model.

The estimated probability of a DLE at each dose level from the model will be summarized using the following intervals:

Target toxicity: [0.00, 0.25)

Over toxicity: [0.25, 1.00]

The BLRM-recommended dose for the next cohort is the highest dose level with posterior probability of the DLE rate falling in the target interval [0.00, 0.25) among the doses fulfilling EWOC. Thus, applying the EWOC criterion it should be unlikely (< 25% posterior probability) that the DLE rate at that dose will exceed 0.25. However, the allowed dose increment will always be the next higher pre-planned dose. However, the maximum allowable dose increment for the subsequent cohort will be no more than 250% from the previous dose. Dose escalation will continue up to the \blacksquare dose as long as the EWOC criterion for the next dose level is fulfilled. At the final dose, at least 6 treated subjects are required. However, the SMC may decide to include additional number of subjects at this dose level.

Since a Bayesian approach is applied, a prior distribution $f(\theta)$ for the unknown parameter vector θ needs to be specified. This prior distribution will be specified as a mixture of three multivariate normal distributions, i.e.

$$f(\theta) = a_1 f_1(\theta) + a_2 f_2(\theta) + a_3 f_3(\theta)$$

with a_i , $i = 1, 2, 3$ the prior mixture weights ($a_1 + a_2 + a_3 = 1$), and $f_i(\theta) = \text{MVN}(\mu_i, \Sigma_i)$, the multivariate normal distribution of the i -th component with mean vector μ_i and covariance matrix Σ_i , where

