A summary of the prior distribution is provided in Table 7.1: 1. Additionally, the prior probabilities of DLEs at different doses, as well as the corresponding probability of targeted and overdosing, are shown in Table 7.1: 2. Graphically, the prior medians with accompanying 95% credible intervals are shown in Figure 7.1: 1. As can be seen from both Table 7.1: 2 and Figure 7.1: 1, the prior medians of the DLE probabilities are in line with the prior medians derived from the weakly informative prior, and the uncertainty around the medians is relatively large, showing the medium amount of information this prior provides. This is also supported by the prior sample size, i.e. the information contained in the prior. This is approximately equal to 3.7 subjects. A detailed evaluation of the model using hypothetical data scenarios and operating characteristics is provided in Appendix 10.3.

Table 7.1: 1 Summary of prior distribution

Prior Component	Mixture Weight	Mean Vector	SD Vector	Correlation
1: Weakly inf.	0.900	-2.197, 0.052	1.2, 1.5	0
2: High Tox.	0.050	-0.847, -0.176	2, 1	0
3: Low Tox.	0.050	-4.595, 0.362	2, 1	0

Table 7.1: 2 Prior probabilities of DLEs at selected doses

Dose	Probability of true DLE rate		mean	sd	Quantiles		
	(0-0.25]	[0.25-1]			2.50%	50%	97.50%
	0.950	0.050	0.054	0.104	0.000	0.013	0.361
	0.927	0.073	0.073	0.120	0.000	0.027	0.428
	0.810	0.190	0.153	0.160	0.006	0.098	0.608

Median (95% CrI)

[figure not shown]

Figure 7.1: 1 Prior medians and 95% credible intervals

The prior may be updated once the trial has started in case new data that can be used will be available. Only subjects for which the occurrence of DLEs within the evaluation period can be evaluated will be considered. The prior that is used for each BLRM analysis for the SMC meetings will be documented in the SMC minutes, the prior used for the final analysis will be documented in the TSAP in case a different prior than described above will be used.

The MFD may be considered reached if all of the following criteria are fulfilled:

- Next recommended dose by the BLRM = current dose
- At least 12 subjects have been treated in the trial.
- At least 6 subjects have been treated at the MFD.

Part B:

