10.3 STATISTICAL APPENDIX

A BLRM with overdose control will be used to guide dose escalation in this study. The BLRM is introduced in Section 7.1, which also specifies the prior for the model. After subjects in each cohort have completed the evaluation period, the prior distribution will be updated through Gibbs sampling procedures with the accumulated DLE data from the evaluation period. Posterior probabilities for the rate of DLEs will be summarized from the BLRM. Selection of the next dose will be based on these probabilities as well as on other safety and laboratory data.

The purpose of this statistical appendix is to present performance metrics (operating characteristics) that illustrate the precision of the design in estimating the MFD (see Section 3.1) under various dose-toxicity relationships through computer simulation. These results are summarized in Table 10.3: 3. In addition, recommendations of the next dose level by the BLRM with overdose control principle are provided under various hypothetical outcome scenarios in early cohorts, to show how it facilitates on-study dose-escalation decisions (see Table 10.3: 1). For simplicity reasons, a cohort size of 3 subjects who are all evaluable is assumed.

Hypothetical data scenarios

Hypothetical data scenarios are shown in Table 10.3: 1. These scenarios reflect potential on-study data constellations and related escalation as allowed by the model and the planned dose groups. For each scenario, the probability of overdose for the current dose, as well as the next potential dose and related probabilities of target dosing and over-dosing are shown (probability of over-dosing: P(OD), probability of target dosing: P(TD)).

For example, scenario 1 represents the case that no DLE is observed in 3 subjects at the starting dose of [REDACTED]. In this case, the next planned dose permitted by the model is 1 mg.

In scenario 6, there is no DLE after the first 2 dose groups, which would allow the trial to continue to the next dose level. If no further DLE occurs in the trial (scenario 13), dose escalation would proceed to the [REDACTED] dose, with an additional cohort at that dose level at the end, i.e. overall 12 subjects.

Table 10.3: 1 Hypothetical data scenarios

Scenario	# Pat.	# DLE	[REDACTED]	[REDACTED]	[REDACTED]
1	3	0	[REDACTED]	[REDACTED]	[REDACTED]
2	3	1	[REDACTED]	[REDACTED]	[REDACTED]
3	3	2	[REDACTED]	[REDACTED]	[REDACTED]
4	6	1	[REDACTED]	[REDACTED]	[REDACTED]

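### Section 3.3.5 has no DLE exception for a missed visit, so read literally an observed Part A DLE could be left out of the BLRM, while Sections 3.1 and 10.3 imply it counts (minor)

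*Protocol*

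**What the plan says.** Protocol Section 3.3.5 (Part A) names two groups that are not evaluable for a DLE. The first is "Subjects withdrawn before visit 4 for another reason than DLE", which carries its own DLE exception. The second has none: "subjects who miss any visit from Visit 2 up to and including Visit 4 are not evaluable for the occurrence of a DLE". Both groups are replaced by default. The SMC may decide otherwise, but that power is written for replacement, not for evaluability. The closing sentence, "Subjects who come off study due to a DLE will not be replaced", protects only subjects who leave the study.

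Section 7.1 sets the model's data rule: "Only subjects for which the occurrence of DLEs within the evaluation period can be evaluated will be considered". It also sets the EWOC limit, under which "it should be unlikely (< 25% posterior probability) that the DLE rate at that dose will exceed 0.25".

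Two places point the other way. Section 3.1 times the model update as "After all subjects in a cohort have either experienced a DLE or have been observed for at least the 7 days evaluation period", so full observation is asked only of DLE-free subjects. Section 10.3 says that "the prior distribution will be updated through Gibbs sampling procedures with the accumulated DLE data from the evaluation period".

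The visible text of the SAP does not settle the matter. Section 6.4 shows no DLE-evaluable set, and Section 7 records that a BLRM analysis was run after each Part A dose group with the protocol's prior.

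**The concern.** Part A is single-dose with follow-up to day 99, so a subject with a DLE can simply stay in follow-up and fall outside the protection for those who leave. Some DLE criteria in Section 5.2.1 can be established at one visit; a loss of more than 15 letters counts at any time-point. A subject who misses Visit 3 and meets that criterion at Visit 4 has a known outcome, yet Section 3.3.5 calls the subject non-evaluable.

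At stake is the overdose probability put to the SMC. Cohorts 1 and 2 are planned at three subjects each, so one event more or less can move that probability across the EWOC limit. The literal rule errs in the unsafe direction: it removes an event and by default replaces the subject.

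**Working it through.** **1. The texts side by side**

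| Part A subject | 3.3.5 with 7.1 | 3.1 with 10.3 |
|---|---|---|
| Withdrawn before Visit 4 because of a DLE | in the model | in |
| Misses Visit 3, DLE at Visit 4, stays in follow-up | out, replaced by default | in |
| DLE at Visit 3, misses Visit 4, stays in follow-up | out, replaced by default | in |

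Rows two and three are the conflict. For a subject with no DLE seen, the missed-visit rule has a purpose: two criteria depend on duration (inflammation for 5 days or more, raised IOP for 3 days), and a missed visit can leave them undetermined.

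**2. Rebuilding the model**

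Model (Section 7.1): logit(π) = log α + β·log(d/d*). The prior is a three-part normal mixture for (log α, log β), with weights 0.90/0.05/0.05, means (−2.197, 0.052), (−0.847, −0.176), (−4.595, 0.362), SDs (1.2, 1.5), (2, 1), (2, 1) and correlation 0.

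The doses are redacted, so only ratios to d* are used. The first component has prior medians 0.02 at the lowest and 0.1 at the highest dose. As −2.197 = logit(0.1), d* is the highest dose. Lowest/highest = exp{[logit(0.02) − logit(0.1)]/exp(0.052)} = exp(−1.695/1.053) = 0.200. The other two components also give 0.200.

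Middle/highest is an assumption. Prior P(π ≥ 0.25) at the middle dose is 0.061, 0.072, 0.084 and 0.096 for ratios 0.3, 0.4, 0.5 and 0.6. Table 7.1: 2 gives 0.073, so 0.4 fits best, and it also reproduces the published median of 0.027.

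Check against Table 7.1: 2: prior P(π ≥ 0.25) at the three doses is 0.050, 0.072, 0.192; published 0.050, 0.073, 0.190.

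**3. Effect of dropping one DLE**

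Posterior P(π ≥ 0.25) is the prior weighted by the product over doses of π^x(1 − π)^(n − x), by numerical integration and checked by Monte Carlo. A dropped subject is taken as replaced by a DLE-free one, because "For any dose-escalation cohort, at least 3 evaluable subjects will be required". A counted subject needs no replacement; the last column applies if one was treated anyway. Ratios are 0.2 : 0.4 : 1 and the limit is 0.25.

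| Run (dose assessed) | DLE dropped | Counted | Counted, replacement also treated |
|---|---|---|---|
| Cohort 1 (middle) | 0/3: 0.027 | 1/3: 0.278 | 1/4: 0.222 |
| Cohort 2 after 0/3 (top) | 0/3: 0.113 | 1/3: 0.314 | 1/4: 0.281 |
| Cohort 3 after 0/3, 0/3; one DLE (top) | 0/6: 0.016 | 1/6: 0.101 | 1/7: 0.078 |
| Cohort 3 after 0/3, 0/3; two DLEs, one dropped (top) | 1/6: 0.101 | 2/6: 0.313 | 2/7: 0.257 |

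Over middle ratios 0.3 to 0.6:
- Cohort 2 always reverses (dropped 0.099 to 0.119; 1/3 0.312 to 0.314; 1/4 0.272 to 0.281).
- Cohort 1 depends on the ratio (1/3: 0.240, 0.278, 0.311, 0.341; 1/4: 0.185, 0.222, 0.255, 0.286).
- Cohort 3 with one DLE never reverses (counted 0.071 to 0.105).
- Cohort 3 with two DLEs reverses at 2/6 throughout (0.291 to 0.322); 2/7 straddles the limit (0.238 to 0.264).

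**4. What was still open**

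Section 1.2 reports seven Part A subjects treated and no DLE when protocol version 4.0 was finalised. Planned cohorts are 3, 3 and 6, filled in order (Section 3.1). As 3 + 3 = 6, the seventh subject is the first of cohort 3.

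**5. Side effect of counting every observed DLE**

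Assume a DLE is seen even if Visit 3 is missed. With true rate p and a proportion m missing Visit 3, the rate among included subjects is p/[p + (1 − p)(1 − m)]. For p = 0.10 and m = 0.10: 0.10/(0.10 + 0.90 × 0.90) = 11.0%. For m = 0.05 it is 10.5%; for m = 0.20, 12.2%.

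**The case against.** The strongest reply is that the exclusion reading is the weaker one. Section 3.3.5 is about replacement. Section 7.1 asks whether DLE occurrence can be evaluated, and an observed DLE has plainly been evaluated. Sections 3.1 and 10.3 agree, and Section 3.3.5 itself twice protects DLE cases. That makes the intent fairly clear, and it stands as a reason to call this a drafting omission. It does not remove the conflict: Section 3.3.5 states non-evaluability in terms, and it writes a DLE exception into one limb and not the other.

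The scenario is also rare. At the prior mean rate of 0.073 for the middle dose, with 5%, 10% or 20% missing Visit 3 independently, the chance of at least one such subject among three is 1 − (1 − 0.073m)³ = 1.1%, 2.2% or 4.3%.

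Other safeguards stand outside the model. The SMC receives a DLE form for each subject and weighs DLEs directly (Sections 3.1, 4.1.4). DLEs are AESIs (5.2.7.1.4). The stopping rule in 3.3.4.3 applies whatever the BLRM says, though not every DLE would trigger it. All of this stands.

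A reader might infer that the trial escalated on a model from which a DLE had been removed, or that the primary endpoint undercounts DLEs. The documents support neither. No DLE had occurred in the first seven subjects, and the primary count uses the treated set (7.3.2).

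**Conclusion.** The inconsistency is real, confined to the BLRM/EWOC input, and minor. As a property of the rule, one dropped DLE turns an unmet EWOC criterion into a met one in cohort 2 at every middle-dose ratio tried, and can do so in cohort 1 depending on that ratio and on whether a replacement was treated.

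In this trial those two cohorts were probably already complete and DLE-free. That is an inference from planned cohort sizes; replacements or expansion could shift the count. What remains is cohort 3, where one dropped DLE reverses nothing. Only losing one of two DLEs among six would clearly matter, and the decision to start Part B rests on all DLE data in any case (Section 3.1). The BLRM still bears on declaring the MFD.

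The figures rest on the stated prior, the derived ratio of 0.2 and an assumed middle ratio of 0.4, with 0.3 to 0.6 shown. The documents do not give later Part A results, so whether any subject was affected is unknown.

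**What to change.** Since the BLRM runs have been done, the main step belongs in the report: state which subjects entered each run and whether any treated subject with an observed DLE was left out. If one was, rerun that analysis with the subject included and show both results. The check may well find nothing.

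Then reconcile Sections 3.1, 3.3.5 and 7.1 with one clause: a subject with a DLE observed in the 7-day evaluation period is DLE-evaluable and enters the BLRM whatever visits were missed, and the missed-visit rule applies only to subjects without an observed DLE. The treated-set primary count needs no change.

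The cost is one report statement and one clause, plus a rerun only if needed. The downside is that inclusion then depends on outcome for subjects with a missed visit, so the estimated rate is slightly conservative, as step 5 of the working shows.
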